Non-English speaking persons will be eligible for consent and subsequent enrollment once a PPHS/IRB approved consent document in the potential subject's native language is available for use. Non-English speaking patients will be approached for consent by the study PI, Sub-investigator or member of the Research Team that speaks the native language of the potential subject and can provide appropriate informed consent. The consenting process, timing and setting are the same as for English speaking subjects.

Several members of the research team are fluent in Spanish and would be available for the Spanish speaking subjects. In the future, if the situation warrants it, we may utilize an interpreter.

Protocol Title:	Optical Coherence Tomography Predictors of Functionally Significant Side Branch Compromise after Provisional Main Vessel Stenting In Bifurcation Lesions Assessed by Fractional Flow Reserve (ORBID – FFR)
Principal Investigator Name/Contact Info:	[name]./ [name]/ [name]
Primary Contact Name/Contact Info	[name] /[name] / [name] [name] /[name] [name]
Date Revised:	January 19, 2017
Study Number:	HSM# 16-00041/ GCO#1: 16-0204(0001)

13) Process to Document Consent in Writing

Subjects will sign a separate Mount Sinai surgical/procedure informed consent for the PCI procedure.

The standard PPHS consent template will be used in this trial.

Recruiters (PIs, Sub-Investigators and Research Staff Members) will be following and will adhere to "SOP HRP-091 Written Documentation of Consent"

14) Vulnerable Populations

Include	Exclude	Vulnerable Population Type
	X	Adults unable to consent
	X	Individuals who are not yet adults (e.g. infants, children, teenagers)
	X	Wards of the State (e.g. foster children)
	X	Pregnant women
	X	Prisoners

15) Multi-Site Human Research (Coordinating Center)

Not Applicable

16) Community-Based Participatory Research

Not Applicable

17) Sharing of Results with Subjects

Protocol Title:	Optical Coherence Tomography Predictors of Functionally Significant Side Branch Compromise after Provisional Main Vessel Stenting In Bifurcation Lesions Assessed by Fractional Flow Reserve (ORBID – FFR)
Principal Investigator Name/Contact Info:	[name]./ [name]/ [name]
Primary Contact Name/Contact Info	[name] /[name] / [name] [name] /[name] [name]
Date Revised:	January 19, 2017
Study Number:	HSM# 16-00041/ GCO#1: 16-0204(0001)

Not Applicable

18) IRB Review History

Not Applicable

19) Control of Drugs, Biologics, or Devices

Note: The IDS has its own forms that must be completed and a review process that must be followed before the IDS representative will sign off on Appendix B for submission to the PPHS.

Not Applicable.

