Title: Optical Coherence Tomography Predictors of Functionally Significant Side Branch Compromise after Provisional Main Vessel Stenting in Bifurcation Lesion Assessed by Fractional Flow Reserve (ORBID-FFR)

PI: [name]

NCT03115580

Document Date: January 19, 2017

 Mount Sinai	Protocol Title:	Optical Coherence Tomography Predictors of Functionally Significant Side Branch Compromise after Provisional Main Vessel Stenting In Bifurcation Lesions Assessed by Fractional Flow Reserve (ORBID – FFR)
	Principal Investigator Name/Contact Info:	[name]./ [name]/ [contact]
	Primary Contact Name/Contact Info	[name] /[name] / [contact] [name] /[name] [contact]
	Date Revised:	January 19, 2017
	Study Number:	HSM# 16-00041/ GCO#1: 16-0204(0001)

MSSM Protocol Template HRP-503a

Instructions:

1. Prepare a document with the following sections. Note that, depending on the nature of your research, certain sections below may not be applicable. Indicate N/A as appropriate, explaining where possible.
2. For any items described in the sponsor's protocol, grant application or other source documents submitted with the application, you may reference the title and page numbers of these documents rather than cutting and pasting into this document. **Do NOT refer to any derived documents, such as the Sample Consent document, or other internal documents required with the submission.**
3. If you reference page numbers, attach those pages to this protocol.
4. When you write a protocol, keep an electronic copy. You will need to modify this copy when making changes.

Brief Summary of Research (250-400 words):

Protocol Title: Optical Coherence Tomography Predictors of Functionally Significant Side Branch Compromise after Provisional Main Vessel Stenting in Calcific Coronary Artery Disease (CAD) Assessed by Fractional Flow Reserve (ORBID-FFR)

This is a single-center, randomized study in patients with stable coronary artery disease.

1) Objectives:

Research Question:

To analyze the incidence of SB compromise after provisional main vessel stenting in calcified bifurcation lesions of CAD patients, determine the incidence and OCT predictors of functionally significant SB stenosis defined as FFR ≤ 0.8 and to compare the FFR values with 3D-OCT measurements of jailed SB ostium after MV stenting.

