Intravascular imaging has provided new understanding of mechanisms associated with SB compromise following bifurcation PCI. Plaque shift has been traditionally considered as the principal mechanism for side-branch compromise after main vessel intervention. Rotational atherectomy(RA) has been advocated for the treatment of bifurcation lesions, since it can effectively remove plaque with minimal injury to adjacent normal arterial segments and potentially reduce plaque shifting, the “snow plow” effect. Intravascular ultrasound (IVUS) has been used for guidance in bifurcation lesions, aiding the visualization of plaque morphology at the main vessel and the side-branches and helping the selection of stent size and length as well as the selection of stenting strategy. However, due to the low spatial resolution of IVUS, all attempts for three-dimensional visualization have only focused on visualization of the luminal contour and not on the vessel morphology or the vessel-stent interaction. Optical coherence tomography (OCT) has ~10 times higher resolution than IVUS, which allows precise evaluation of the microstructure of the vessel wall including lipid pool, fibrous cap, calcification, and thrombus. OCT has been shown to constitute a valuable tool for PCI guidance and also the utility of three-dimensional (3D) renderings for

Protocol Title:	Optical Coherence Tomography Predictors of Functionally Significant Side Branch Compromise after Provisional Main Vessel Stenting In Bifurcation Lesions Assessed by Fractional Flow Reserve (ORBID – FFR)
Principal Investigator Name/Contact Info:	[name]./ [name]/ [contact]
Primary Contact Name/Contact Info	[name] /[name] / [contact] [name] /[name] [contact]
Date Revised:	January 19, 2017
Study Number:	HSM# 16-00041/ GCO#1: 16-0204(0001)

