Figure 2. 3D quantitative coronary angiography (QCA) and cut-plane analysis of side branch ostium from the main branch OCT pullback for bifurcation PCI before (top row) and after (bottom row) stenting.

We assumed FFR (+) prevalence of either 20% or 25% based on previous studies. We also assumed that there would be a roughly equal proportion of patients with high and lipid levels.

Based on these assumptions, we will need at least 75 patients per EACH high lipid and low lipid groups to detect an odds ratio (OR) of 2.8.

Protocol Title:	Optical Coherence Tomography Predictors of Functionally Significant Side Branch Compromise after Provisional Main Vessel Stenting In Bifurcation Lesions Assessed by Fractional Flow Reserve (ORBID – FFR)
Principal Investigator Name/Contact Info:	[name]./ [name]/ [contact]
Primary Contact Name/Contact Info	[name] /[name] / [contact] [name] /[name] [contact]
Date Revised:	January 19, 2017
Study Number:	HSM# 16-00041/ GCO#1: 16-0204(0001)

The table below is showing the detectable OR we might have under different assumptions of the patient population assuming an equal proportion of high/low lipid level groups.

Prevalence of + FFR	Patients per group	Detectable OR with 80% power
0.2	50	3.7
0.2	75	2.9
0.2	100	2.5
0.25	50	3.5
0.25	75	2.8
0.25	100	2.4

a) Recruitment Methods

We will recruit patients referred to the interventional cardiologists involved on this study based on their medical history who require a PCI of the main vessel with drug eluting stent implantation for the treatment of stable CAD where impact on the side branch can be access. Patients will be undergoing a PCI using an angiography and OCT-guided strategy. Patients will be approached in the ambulatory unit before their procedure to obtain consent and review and confirm the inclusion and exclusion criteria of the protocol.

The PI and the research team will identify potential subjects based on their medical history. Potential patients will be approached in the ambulatory unit before their procedure to obtain consent and check the inclusion/exclusion criteria.

In all cases, the Principal Investigator, Sub-Investigator or member of the Research Team will discuss the research trial and informed consent document in full detail following Good Clinical Practices and HIPAA Laws. During the informed consent process, all of the potential subject's questions will be answered. Subjects will be given a copy of the signed

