Protocol Title:	Optical Coherence Tomography Predictors of Functionally Significant Side Branch Compromise after Provisional Main Vessel Stenting In Bifurcation Lesions Assessed by Fractional Flow Reserve (ORBID – FFR)
Principal Investigator Name/Contact Info:	[name]./ [name]/ [contact]
Primary Contact Name/Contact Info	[name] /[name] / [contact] [name] /[name] [contact]
Date Revised:	January 19, 2017
Study Number:	HSM# 16-00041/ GCO#1: 16-0204(0001)

informed consent document, a copy will be placed in the subject's chart and the original copy will be stored in a secure location in the research office.

b) Inclusion and Exclusion Criteria

1. General inclusion criteria. Subjects will be enrolled in the study, if **ALL** of the following criteria are met

- All patients over 18 years of age presenting with stable coronary artery disease.
- Patients must have a clinical indication for coronary intervention.
- Creatinine Kinase Myocardial-Band Isoenzyme (CK-MB) must be less than or equal to the upper limit of lab normal (ULN) value within eight hours prior to the procedure

2. Angiographic inclusion criteria. Subjects will be enrolled in the study, if **ALL** of the following criteria are met:

- The target lesion must be a *de novo* calcified bifurcation coronary lesion that hasn't been previously treated with any interventional procedure for which provisional main vessel stenting strategy is planned after reviewing angiogram.
- The target vessel must be a native coronary artery with
 - a) stenosis $\geq 70\%$ and $<100\%$, or
 - b) Stenosis $\geq 50\%$ and $<70\%$ with evidence of clinical ischemia via positive stress test, or FFR ≤ 0.8 , or IVUS or OCT minimal lumen area $\leq 4.0 \text{ mm}^2$.
- The target lesion should have SB DS 30 - 70%.
- The target main vessel reference diameter must be $\geq 2.5 \text{ mm}$ and $\leq 4.0 \text{ mm}$.
- The SB reference diameter must be $> 2 \text{ mm}$ by coronary angiogram.
- The target vessel must have a Thrombolysis in Myocardial Infarction (TIMI) flow grade 3 at baseline.

Protocol Title:	Optical Coherence Tomography Predictors of Functionally Significant Side Branch Compromise after Provisional Main Vessel Stenting In Bifurcation Lesions Assessed by Fractional Flow Reserve (ORBID – FFR)
Principal Investigator Name/Contact Info:	[name]./ [name]/ [contact]
Primary Contact Name/Contact Info	[name] /[name] / [contact] [name] /[name] [contact]

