Date Revised:	January 19, 2017
Study Number:	HSM# 16-00041/ GCO#1: 16-0204(0001)

General exclusion criteria: Patient will not be enrolled in the study if ANY of the following criteria are present in the patient.

- Patients with ostial left main artery lesions or ostial right coronary artery lesions
- Female patients with child bearing potential not taking adequate contraceptives or currently breastfeeding
- Known allergy to acetylsalicylic acid or clopidogrel.
- Planned surgery within 12 months.
- History of bleeding diathesis
- Major surgery within 15 days
- Life expectancy < 12 months.
- Patients with kidney dysfunction (CrCl<30)

c) Number of Subjects

One hundred and fifty (150) consecutive patients with lesions requiring PCI of main vessel with drug eluting stent implantation for the treatment of stable CAD will be included in the study.

d) Study Timelines

This is a randomized study with one visit and no clinical follow-ups.

e) Study Endpoints

The primary endpoint is SB compromise defined as SB DS \geq 70%, or dissection or TIMI < 3.

The secondary endpoints

- SB FFR after main vessel stenting and its correlation with OCT imaging parameters before PCI
- OCT predictors of SB TIMI flow reduction after main vessel PCI
- Off-line analysis of SB stenosis by 3D-OCT and its correlation with FFR; correlation between 3D-QCA measurements, 3D-OCT, and FFR data.

Protocol Title:	Optical Coherence Tomography Predictors of Functionally Significant Side Branch Compromise after Provisional Main Vessel Stenting In Bifurcation Lesions Assessed by Fractional Flow Reserve (ORBID – FFR)
Principal Investigator Name/Contact Info:	[name]./ [name]/ [contact]
Primary Contact Name/Contact Info	[name] /[name] / [contact] [name] /[name] [contact]
Date Revised:	January 19, 2017
Study Number:	HSM# 16-00041/ GCO#1: 16-0204(0001)

- Association between calcification assessment by angiography and OCT imaging.
- FFR Device Success (ability to successfully deliver FFR wire to desired SB distal segment [n/150]).
- FFR Wire Workhorse Capability (proportion of patients [n/150] in which FFR wire able to serve as rail to deliver additional interventional devices to target SB lesion).

f) Procedures Involved in the Human Research

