Stable CAD patients with bifurcation lesions in whom provisional stenting strategy is planned, who have moderate or severe calcification in the main vessel lesion identified by angiography, SB stenosis 30-70% and SB reference diameter > 2mm will be enrolled in the study.

Moderate calcification will be defined as radiopaque density observed only during the cardiac cycle and typically involving only one side of the vascular wall, and severe calcification will be defined as radiopaque density noted without cardiac motion prior to contrast injection and involving both sides of the arterial wall. After completion of diagnostic angiogram and confirmation of subject eligibility, subjects will be randomly assigned to Rotational atherectomy (RA or Cutting Balloon Angioplasty (CBA)/PTCA group in a 1:1 fashion.

Patients in both groups will undergo PCI with stent implantation according to current standards of care. Lesion preparation including lesion pre-dilation, scoring or sculpting balloon angioplasty, and use of atherectomy and protection devices will be performed at the operator's discretion, followed by MV stenting. The operator will also decide in both groups about the length and size of the implanted stent. Procedural optimization, such as post-dilation or additional stent implantation will be performed based only on the angiographic findings, according to the discretion of the operator.

Protocol Title:	Optical Coherence Tomography Predictors of Functionally Significant Side Branch Compromise after Provisional Main Vessel Stenting In Bifurcation Lesions Assessed by Fractional Flow Reserve (ORBID – FFR)
Principal Investigator Name/Contact Info:	[name]./ [name]/ [contact]
Primary Contact Name/Contact Info	[name] /[name] / [contact] [name] /[name] [contact]
Date Revised:	January 19, 2017
Study Number:	HSM# 16-00041/ GCO#1: 16-0204(0001)

Optical coherence tomography (OCT) is an established medical imaging technique that uses light to capture micrometer-resolution, three-dimensional images from within optical scattering media will be performed to analyze plaque morphology, the extent and location of calcification, side branch size, angle, and ostial involvement.

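### The trial randomises lesion preparation 1:1, but no objective, endpoint or analysis uses the assigned arm, although the arm can affect both the pre-stent OCT reading and the outcome

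*Combined protocol and SAP*

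**What the plan says.** - **Aim.** Section 1) Objectives: "To analyze the incidence of SB compromise after provisional main vessel stenting in calcified bifurcation lesions of CAD patients". It goes on to the incidence and OCT predictors of a side-branch FFR of 0.8 or below, and a comparison of FFR with 3D-OCT. RA and CBA/PTCA are not mentioned.
- **Allocation.** Section 5 f): "subjects will be randomly assigned to Rotational atherectomy (RA or Cutting Balloon Angioplasty (CBA)/PTCA group in a 1:1 fashion".
- **Reason the arms may differ.** Section 2) Background names plaque shift as the mechanism traditionally held mainly responsible for side-branch compromise, and says of RA that "it can effectively remove plaque with minimal injury to adjacent normal arterial segments and potentially reduce plaque shifting".
- **Endpoints.** Section 5 e): "The primary endpoint is SB compromise defined as SB DS" of at least 70%, or dissection, or TIMI flow below 3. The secondary endpoints include side-branch FFR and its correlation with OCT, and OCT predictors of reduced side-branch TIMI flow. None is by arm.
- **Analysis and sample size.** Data analysis and Statistical methods names a t-test and correlations. The sample size compares high-lipid with low-lipid patients: "We assumed FFR (+) prevalence of either 20% or 25% based on previous studies". Section 5 c) enrols "One hundred and fifty (150) consecutive patients".
- **Timing.** Section 5 f) takes the OCT-PRE pullback once the lesion has been prepared and before the stent is placed. Side-branch FFR is measured only when the angiogram shows none of the three components of compromise.
- **Delivered preparation.** Section 5 f) also says, for both groups, "use of atherectomy and protection devices will be performed at the operator's discretion".

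**The concern.** Two things are at stake.

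**The incidence.** If the arms differ on the primary endpoint, a single pooled incidence is an average that does not show it. The protocol gives a reason why they might. The comparison that randomisation makes possible would then go unreported.

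**The predictors.** Randomisation balances what exists before allocation. OCT-PRE comes after the allocated step. RA removes plaque, so the arm could change what OCT shows and also change the risk of the outcome. An analysis that ignores arm can then credit the OCT feature with an association that belongs to the preparation, or can mask a real one.

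**Working it through.** **1. The plan's own figure.** The sample size gives 75 per lipid group for an odds ratio (OR) of 2.8 at 25% FFR-positive with 80% power. Alpha is not stated; take two-sided 0.05, and treat 25% as the low-lipid rate.
- High-lipid odds = (0.25/0.75) × 2.8 = 0.933, so p2 = 0.933/1.933 = 0.483, the difference d = 0.233 and the mean rate is 0.366.
- n = [1.96·√(2 × 0.366 × 0.634) + 0.842·√(0.25 × 0.75 + 0.483 × 0.517)]² / d² ≈ 66.1, that is 67 per group.
- With continuity correction, (n/4)·[1 + √(1 + 4/(n·d))]² ≈ 74.4, that is 75.

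The stated figure reproduces. It does not involve the randomised arms; 75 per arm is simply 150/2.

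**2. Assumed inputs.** The documents give no side-branch-compromise rate, no RA effect and no effect of preparation on OCT lipid class. I take arm risks of 15% v 25% and 10% v 30%. Both average 20%, the lower prevalence used in the sample size. That prevalence is for FFR, so using it for the primary endpoint in step 3 is a further assumption.

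**3. Pooled and by-arm precision.** Half-width = 1.96·√(p(1−p)/n).
- Pooled: 20%, n = 150, ±6.4 points.
- By arm, n = 75: 15% ± 8.1 and 25% ± 9.8; or 10% ± 6.8 and 30% ± 10.4.
- Risk difference, 15% v 25%: SE = √(0.1275/75 + 0.1875/75) = 0.0648, so 10 points, 95% CI about −3 to 23.
- Risk difference, 10% v 30%: SE = √(0.09/75 + 0.21/75) = 0.0632, so 20 points, 95% CI about 8 to 32.

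With pooled rates of 20 to 25%, power for the arm comparison at 75 per arm is 16–19% for an arm OR of 1.5, 38–44% for 2 and 68–75% for 2.8.

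**4. Predictor bias when arm shifts the OCT reading.** Suppose lipid class has no effect within either arm, the arms are equal in size, and high lipid is read in 40% of the lower-risk arm and 60% of the higher-risk arm.
- 15% v 25%: risk if high = 0.4 × 0.15 + 0.6 × 0.25 = 0.21; risk if low = 0.6 × 0.15 + 0.4 × 0.25 = 0.19. Crude OR = (0.21/0.79)/(0.19/0.81) = 1.13.
- 10% v 30%: 0.22 against 0.18. Crude OR = (0.22/0.78)/(0.18/0.82) = 1.28.
- Shift reversed: 1/1.13 = 0.88 and 1/1.28 = 0.78.
- Within each arm the OR is 1.0 by construction, so adjusting for arm recovers 1.0.

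As a sensitivity range, arm ORs of 1.5 to 2.8 around a 25% rate with shifts of 10 to 30 points give 1.04 to 1.35 (reversed, 0.96 to 0.74).

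**5. No shift.** If arm does not alter the OCT class, omitting an arm effect of OR 1.5 to 2.8 moves a lipid OR of 2.8 only to between 2.78 and 2.68.

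**The case against.** The strongest reply is that little follows from the plan's silence. A pooled incidence over the enrolled patients is a legitimate estimate. The Background says only that RA may potentially reduce plaque shift; it states no hypothesis and no effect size. No predictor model is specified, so no covariate has been rejected. The bias figures rest on assumed inputs, and 10% v 30% is an arm OR of (0.30/0.70)/(0.10/0.90) = 3.86, larger than the 2.8 on which the trial is sized. All of that stands, and it limits the point.

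A reader might infer more than the text supports:
- *That the protocol expects the arms to differ, so the pooled figure describes neither.* The text says only potentially. At arm ORs of 1.5 to 2, each arm's rate lies within or about at the pooled half-width of 6.4 to 6.9 points.
- *That the design fixes a 1:1 mix of preparations.* It fixes the assignment. Section 5 f) leaves preparation, atherectomy included, to the operator in both groups, so the delivered mix is open.
- *That predictors of the composite primary endpoint are biased.* The listed predictor analyses concern FFR and side-branch TIMI flow.
- *That the entry rule "The target lesion should have SB DS 30 - 70" percent invalidates the incidence.* It is stated openly and defines the eligible population; at most the aim could be worded more narrowly.

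Figure 1 under Study Design was not available and is not relied on. What the reply does not answer is that the written plan, followed as it stands, never uses the randomised contrast and does not provide for adjusting a predictor measured after randomisation.

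**Conclusion.** The concern holds in a limited form and is worth a change to the plan. No objective, endpoint, named test or sample-size input uses the assigned arm, and OCT-PRE follows the randomised step.

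The size cannot be established from the documents. Under the assumed 20-point shift, a null lipid effect appears as a crude OR of about 1.13 to 1.28, or 0.88 to 0.78 in the other direction. That is modest beside the 2.8 the trial is sized on, and the bias is small if preparation does not alter the OCT reading. These ORs assume equal arms in the analysed set. Because FFR is measured only in patients without compromise, arm could also affect who enters the FFR analyses.

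By-arm results will describe assignment. Unless the operator-discretion text is reconciled with it, they need not describe the preparation delivered, and adjusting for assigned arm may remove only part of any bias.

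**What to change.** - **Study Endpoints and Data analysis:** report the primary endpoint by assigned arm (events and number per arm, 95% CI, and risk difference with 95% CI) beside the pooled figure. Present the contrast as estimation, because power is limited.
- **Predictor analyses:** include assigned arm as a covariate in the listed analyses of side-branch FFR, FFR of 0.8 or below, and side-branch TIMI flow reduction.
- **Objectives:** state the RA versus CBA/PTCA comparison in the research question.
- **Procedures:** reconcile the randomised assignment with the statements leaving preparation, including atherectomy, to the operator in both groups, and say that by-arm results are by assignment.

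The statistical changes affect analysis and wording only, and need no new patients or measurements. The downside is wider intervals: on the assumed rates, about ±7 to ±10 points per arm against ±6.4 pooled.

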 Mount Sinai	Protocol Title:	Optical Coherence Tomography Predictors of Functionally Significant Side Branch Compromise after Provisional Main Vessel Stenting In Bifurcation Lesions Assessed by Fractional Flow Reserve (ORBID – FFR)
	Principal Investigator Name/Contact Info:	[name]./ [name]/ [name]
	Primary Contact Name/Contact Info	[name] /[name] / [name] [name] /[name] [name]
	Date Revised:	January 19, 2017
	Study Number:	HSM# 16-00041/ GCO#1: 16-0204(0001)

Data analysis and Statistical methods:

T-test will be used. OCT off-line image analysis. For the accurate characterization of bifurcation lesions, OCT images will be analyzed systematically at 1 mm intervals according to previously validated criteria for plaque characterization using the St. Jude Medical Offline Review Workstation as we described previously. In addition, three-dimensional OCT software (QAngio OCT, Medis) will be used to obtain the information for the side branch ostium from a single main branch pullback as described recently in a validation of cut plane analysis (Figure 2). We will also perform three-dimensional quantitative coronary angiography (3D-QCA) using QAngio XA 3D software (Medis) to obtain the measurements of bifurcation angles, stenosis, and references. This software is dedicated to bifurcation lesions and has shown to provide highly accurate assessment of lesion dimensions and geometry based on 3D reconstruction of bifurcation lesions. Offline analysis of side branch for impingement of the ostium of SB leading to acute loss in SB diameter, area, carina shift and plaque shift will be performed and 3D-OCT parameters will be correlated with SB FFR measurements.

 Mount Sinai	Protocol Title:	Optical Coherence Tomography Predictors of Functionally Significant Side Branch Compromise after Provisional Main Vessel Stenting In Bifurcation Lesions Assessed by Fractional Flow Reserve (ORBID – FFR)
	Principal Investigator Name/Contact Info:	[name]./ [name]/ [contact]
	Primary Contact Name/Contact Info	[name] /[name] / [contact] [name] /[name] [contact]
	Date Revised:	January 19, 2017
	Study Number:	HSM# 16-00041/ GCO#1: 16-0204(0001)

[figure not shown]

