Patients in both groups will undergo (standard of care) a percutaneous coronary intervention (PCI), also known as coronary angioplasty, is a nonsurgical technique for treating obstructive coronary artery disease, including unstable angina, acute myocardial infarction (MI), and multivessel coronary artery disease (CAD) with stent implantation according to current standards of care. Lesion preparation including lesion pre-dilation, scoring or sculpting balloon angioplasty, and use of atherectomy (a minimally invasive endovascular surgery technique for removing atherosclerosis from blood vessels within the body.) and protection devices will be performed at the operator's discretion, followed by MV stenting.

The operator will also decide in both groups about the length and size of the implanted stent. Procedural optimization, such as post-dilation or additional stent implantation will be performed based only on the angiographic findings, according to the discretion of the operator.

The Pre and post stenting OCT + FFR for side branch are the research procedures.

OCT pullback will be performed after lesion preparation before stenting (OCT-PRE) and after PCI (OCT-POST). FFR measurement in the side branch will be performed, if the coronary angiogram shows SB DS < 70%, TIMI grade 3 flow and no dissection in the side branch.

To perform FFR measurements, the pressure wire will be passed through the struts of the MV stent into the SB and FFR will be measured at least 5 mm distal to the jailed SB stenosis. Adenosine will be infused through the

Protocol Title:	Optical Coherence Tomography Predictors of Functionally Significant Side Branch Compromise after Provisional Main Vessel Stenting In Bifurcation Lesions Assessed by Fractional Flow Reserve (ORBID – FFR)
Principal Investigator Name/Contact Info:	[name]./ [name]/ [contact]
Primary Contact Name/Contact Info	[name] /[name] / [contact] [name] /[name] [contact]
Date Revised:	January 19, 2017
Study Number:	HSM# 16-00041/ GCO#1: 16-0204(0001)

femoral vein at least 140 µg/kg per minute to induce maximal coronary blood flow.

g) Specimen Banking

Not Applicable

h) Data Management and Confidentiality

Confidentiality of subject medical information will be ensured by providing unique identifiers (Subject ID) for data transmitted from the enrolling centers to St. Jude Medical Center. Designated representatives will not receive identifiable subject information.

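### The FFR-positive comparison is sized on all 150 patients, but FFR is measured only in patients without the primary endpoint, and the one named test gives neither odds ratio

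*Combined protocol and SAP*

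**What the plan says.** - **Analysis** (section 5, Data analysis and Statistical methods): the only named test is "T-test will be used", with no outcome or groups. The rest of that text describes image analysis, plus a correlation of 3D-OCT parameters with SB FFR by an unnamed method.
- **Sample size** (same section): "We assumed FFR (+) prevalence of either 20% or 25% based on previous studies", and on that basis "we will need at least 75 patients per EACH high lipid and low lipid groups to detect an odds ratio (OR) of 2.8". The table gives detectable ORs at 80% power for 50, 75 and 100 per group. Section 5 c) sets enrolment at 150.
- **Primary endpoint** (5 e, Study Endpoints): "The primary endpoint is SB compromise defined as SB DS" of at least 70%, or dissection, or TIMI flow below 3. It is yes/no.
- **FFR measurement** (5 f, Procedures): "FFR measurement in the side branch will be performed, if the coronary angiogram shows SB DS < 70%, TIMI grade 3 flow" and no dissection.
- **Design** (5 f): "subjects will be randomly assigned to Rotational atherectomy" or cutting balloon/PTCA, 1:1.
- **Objectives** (section 1): the incidence of SB compromise, and the incidence and OCT predictors of FFR ≤ 0.8.
- **Background** (section 2): the previous 30-patient study suggested that high lipid content of the main-vessel lesion may contribute to SB ostial stenosis.

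**The concern.** The condition for measuring FFR is the negation of the primary endpoint. A patient who has the primary event has no FFR result, so cannot be FFR-positive or FFR-negative. The sample-size text makes no allowance for this, and nothing says whether such patients count as positive, negative or excluded.

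Two things follow. The sized comparison will have fewer than 75 per group unless there are no primary events. Its result also applies only to patients without SB compromise. Because lipid content is suspected of contributing to SB stenosis, the loss may differ between the groups being compared.

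Alongside this, the trial is sized on an odds ratio that no stated analysis produces, and the yes/no primary endpoint has no stated analysis, by arm or otherwise. The choice is left open until the data are in hand.

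**Working it through.** **1. The two conditions.** Primary endpoint: DS ≥ 70%, or dissection, or TIMI < 3. Its negation: DS < 70%, no dissection, and TIMI 3. That is the FFR rule in 5 f). So FFR-evaluable patients = 150 × (1 − c) at most, where c is the primary event rate.

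**2. Reproduce the plan's figure.** Inputs from the plan: 25% prevalence, OR 2.8, 80% power, equal groups. Assumed, because not stated: two-sided 5%, and prevalence taken as the low-lipid group's rate.

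- High-lipid rate: odds = (0.25/0.75) × 2.8 = 0.933, so p₂ = 0.933/1.933 = 0.483. Difference d = 0.233, mean rate 0.366.
- Uncorrected: n₀ = [1.96·√(2 × 0.366 × 0.634) + 0.842·√(0.25 × 0.75 + 0.483 × 0.517)]² / d² = 66.1, so 67 per group.
- Continuity-corrected: n = (n₀/4)·[1 + √(1 + 4/(n₀d))]² = 74.4, so **75 per group**, the plan's figure.

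Solving the corrected formula for the OR gives:

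| Prevalence | n per group | Plan | Recomputed |
|---|---|---|---|
| 20% | 50 / 75 / 100 | 3.7 / 2.9 / 2.5 | 3.72 / 2.94 / 2.55 |
| 25% | 50 / 75 / 100 | 3.5 / 2.8 / 2.4 | 3.52 / 2.79 / 2.43 |

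Agreement is within about 0.05 throughout. The table therefore assumes an FFR result in all 75 per group.

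**3. Remove the patients without FFR.** The documents give no primary event rate, so c is assumed. n per group = 75 × (1 − c). Power is at OR 2.8 in the 25% row.

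| c | Evaluable | Detectable OR, 25% row | Detectable OR, 20% row | Power, corrected | Power, uncorrected |
|---|---|---|---|---|---|
| 0 | 150 | 2.79 | 2.94 | 80% | 85% |
| 5% | 142.5 | 2.86 | 3.02 | 78% | 83% |
| 10% | 135 | 2.95 | 3.11 | 75% | 81% |
| 20% | 120 | 3.15 | 3.32 | 70% | 76% |
| 30% | 105 | 3.42 | 3.61 | 63% | 70% |

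Uncorrected power crosses 80% at c of about 12%.

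**4. Unequal loss.** If 10% of low-lipid and 30% of high-lipid patients have the event, 67.5 and 52.5 remain and the detectable OR is 3.17, against 3.15 for an equal 20% loss. Imbalance barely changes power; its importance is for interpretation.

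**5. The named test.** Applied to continuous OCT or FFR values, a t-test gives a difference in means. Applied to 0/1 data it gives at best a difference in proportions. Neither it nor a correlation gives an odds ratio with a confidence interval.

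**The case against.** **The loss is conditional and may be small.** The event rate is assumed. The corrected figures carry a continuity correction that a logistic analysis would not use; without it, power is still 81% at 10% events. This stands. A reader might infer that the trial is underpowered, but the documents do not support that without an event rate. They support only that the stated figure presumes FFR in everyone.

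**The table already shows the sensitivity.** The worst case above, 52.5 per group with ORs of 3.42 and 3.61, lies just inside the plan's rows for 50 per group (3.5 and 3.7). That is fair. What is missing is any link between those rows and the FFR rule, and the text commits to 75 per group.

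**A t-test is not invalid here.** On 0/1 data at this size it roughly keeps its error rate, and it suits continuous measures. It is the only named test, not the only analysis. A reader might infer inflated false positives; nothing supports that. The gap is the missing odds ratio and the missing link to an outcome.

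**Other tempting inferences.** The device endpoint "FFR Device Success (ability to successfully deliver FFR wire to desired SB distal segment [n/150"] could be read as proof that the FFR rule was overlooked. It concerns wire delivery, and the neighbouring endpoint uses the wire as a rail for devices to the side branch, so 150 may be intended. Selection or confounding in the lipid contrast is possible, but its size cannot be stated from the documents. Nor is the lack of adjustment for baseline SB stenosis an error: any gain rests on how prognostic it is, which the documents do not say.

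**Conclusion.** The point holds. The sized population (150 with FFR) is not the population measured (those without the primary endpoint), and no stated analysis yields the odds ratio the trial is sized on or one for the primary endpoint. The direction is certain: any primary event reduces the FFR comparison and makes it conditional on no SB compromise. The size is not. Over assumed event rates of 5–30% the detectable OR is 2.86–3.42 instead of 2.8, and power at OR 2.8 is 78–63% with continuity correction or 83–70% without. These figures also rest on two-sided 5% and on reading the prevalence as the low-lipid rate, the reading that reproduces the table. This should be corrected before analysis; it does not make the trial uninformative.

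**What to change.** Replace "T-test will be used" with:

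> The incidence of SB compromise (all patients) and of FFR ≤ 0.80 (FFR-evaluable patients) will be reported with 95% CI. SB compromise will be compared between randomised arms, and FFR ≤ 0.80 between high and low lipid groups, by logistic regression with ORs and 95% CI; the unadjusted OR is reported for the lipid comparison because the sample size rests on it. FFR analyses are restricted to patients with post-stent SB DS < 70%, TIMI 3 and no dissection, and are labelled as conditional on no SB compromise. T-tests are limited to continuous measures.

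Restate the detectable OR, or the power, for the expected number of FFR-evaluable patients at a stated event rate. Whether the arm comparison is the primary test is for the investigator to state. Adjustment for baseline SB stenosis is optional.

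**Cost:** protocol wording and one restated table, with no extra patients or procedures and no change to the FFR measurement rule. The downside is a less favourable detectable OR. Holding 150 evaluable patients would instead need 150/(1 − c) enrolled, about 158, 167, 188 or 215 at 5, 10, 20 or 30% events; that is not proposed.
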